### **6.3     *Subject Population(s) for Analysis***

All treated subjects in study.

## **7     *Safety and Adverse Events***

### **7.1 *Definitions***

#### **Unanticipated Problems Involving Risk to Subjects or Others**

Any incident, experience, or outcome that meets all of the following criteria:

- Unexpected in nature, severity, or frequency (i.e. not described in study-related documents such as the IRB-approved protocol or consent form, the investigators brochure, etc)
- Related or possibly related to participation in the research (i.e. possibly related means there is a reasonable possibility that the incident experience, or outcome may have been caused by the procedures involved in the research)
- Suggests that the research places subjects or others at greater risk of harm (including physical, psychological, economic, or social harm).

#### **Adverse Event**

An *adverse event* (AE) is any symptom, sign, illness or experience that develops or worsens in severity during the course of the study. Intercurrent illnesses or injuries should be regarded as adverse events. Abnormal results of diagnostic procedures are considered to be adverse events if the abnormality:

- results in study withdrawal
- is associated with a serious adverse event
- is associated with clinical signs or symptoms
- leads to additional treatment or to further diagnostic tests
- is considered by the investigator to be of clinical significance

An Adverse Event (AE) is defined as any new untoward medical occurrence or worsening of a preexisting medical condition in a clinical investigation participant administered study drug and that does not necessarily have a causal relationship with this treatment. An AE can therefore be any unfavorable and unintended sign (such as an abnormal laboratory finding), symptom, or disease temporally associated with the use of investigational product, whether or not considered related to the investigational product.

The causal relationship to study drug is determined by a physician and should be used to assess all adverse events (AE). The causal relationship can be one of the following:

Related: There is a reasonable causal relationship between study drug administration and the AE.

Not related: There is not a reasonable causal relationship between study drug administration and the AE.

The term "reasonable causal relationship" means there is evidence to suggest a causal relationship.

Adverse events can be spontaneously reported or elicited during open-ended questioning, examination, or evaluation of a subject. (In order to prevent reporting bias, subjects should not be questioned regarding the specific occurrence of one or more AEs.)

### **Serious Adverse Event**

Adverse events are classified as serious or non-serious. A *serious adverse event* is any AE that is:

- fatal
- life-threatening (defined as an event in which the participant was at risk of death at the time of the event; it does not refer to an event which hypothetically might have caused death if it were more severe)
- requires or prolongs hospital stay
- results in persistent or significant disability or incapacity
- a congenital anomaly or birth defect
- an important medical event (defined as a medical event(s) that may not be immediately life-threatening or result in death or hospitalization but, based upon appropriate medical and scientific judgment, may jeopardize the subject or may require intervention [eg, medical, surgical] to prevent one of the other serious outcomes listed in the definition above.) Examples of such events include, but are not limited to, intensive treatment in an emergency room or at home for allergic bronchospasm; blood dyscrasias or convulsions that do not result in hospitalization.)
- Suspected transmission of an infectious agent (eg, pathogenic or nonpathogenic) via the study drug is an SAE.

Important medical events are those that may not be immediately life threatening, but are clearly of major clinical significance. They may jeopardize the subject, and may require intervention to prevent one of the other serious outcomes noted above. For example, drug overdose or abuse, a seizure that did not result in in-patient hospitalization, or intensive treatment of bronchospasm in an emergency department would typically be considered serious.

Although pregnancy, overdose, potential drug-induced liver injury (DILI), and cancer are not always serious by regulatory definition, these events must be handled as SAEs.

Any component of a study endpoint that is considered related to study therapy should be reported as an SAE (e.g., death is an endpoint, if death occurred due to anaphylaxis, anaphylaxis must be reported).

All adverse events that do not meet any of the criteria for serious should be regarded as *non-serious adverse events*.

## **NONSERIOUS ADVERSE EVENT**

- Non-serious Adverse Events (AE) are to be provided to BMS in aggregate via interim or final study reports as specified in the agreement or, if a regulatory requirement [e.g., IND US trial] as part of an annual reporting requirement.
- Non-serious AE information should also be collected from the start of a placebo lead-in period or other observational period intended to establish a baseline status for the subjects.

A *non-serious adverse event* is an AE not classified as serious.

### **Non-serious Adverse Event Collection and Reporting**

The collection of non-serious AE information should begin at initiation of study drug. All non-serious adverse events (not only those deemed to be treatment-related) should be collected continuously during the treatment period and for a minimum of **30** days following the last dose of study treatment.

Non-serious AEs should be followed to resolution or stabilization, or reported as SAEs if they become serious. Follow-up is also required for non-serious AEs that cause interruption or discontinuation of study drug and for those present at the end of study treatment as appropriate.

### **Adverse Event Reporting Period**

The study period during which adverse events must be reported is normally defined as the period from the initiation of any study procedures to the end of the study treatment follow-up. For this study, the study treatment follow-up is defined as 30 days following the last administration of study treatment.

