**REMISSION OR LOW DISEASE ACTIVITY TABLE OF EVENTS**

Procedure	Screening Period	DAY 1	WEEK 2	MONTH 1, 2, 3,4,5	MONTH 6/ET	MONTH 9	FOLLOW-UP (WEEK 48-52)
Medication review	X	X	X			X	X
Review of side effects	X	X					
Physical examination	X	X			X		
Height (screening only) & weight	X	X	X	X	X		
Blood sample(s) (Approx.166-176 - ml, or - 12tablespoons per visit)	X	X	X	X	X	X	
Urine sample	X	X	X	X	X		
Pregnancy test for women who can become pregnant	X	X	X	X			
Vital signs (temperature, blood pressure, heart rate (pulse))	X	X	X	X	X		
Assessments of your tender and swollen joints	X	X	X	X	X	X	
Assessments of disease activity	X	X	X	X	X	X	
Your Assessment of pain	X	X	X	X	X	X	
Rapid 3 patient questionnaire	X	X	X	X	X		
Abatacept infusion		X	X	X			
Adverse events		X		X	X	X	X

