#### Age and Reproductive Status

- a) Men and women, age's  $\geq 18$  years (or age of majority)
- b) Women of childbearing potential (WOCBP) must have a negative serum or urine pregnancy test (minimum sensitivity 25 IU/L or equivalent units of HCG) within 24 hours prior to the start of study drug.
- c) Women must not be breastfeeding and must agree not to breastfeed during the study and for 100 days thereafter
- d) WOCBP must agree to follow instructions for method(s) of contraception for the duration of treatment with study drug plus 5 half-lives of study drug (70 days) plus 30 days (duration of ovulatory cycle) for a total of 100 days post-treatment completion.
- e) Males who are sexually active with WOCBP must agree to follow instructions for

method(s) of contraception for the duration of treatment with study drug, plus 5 half-lives of the study drug (70 days) plus 90 days (duration of sperm turnover) for a total of 160 days post-treatment completion.

f) Azoospermic males and WOCBP who are continuously not heterosexually active are exempt from contraceptive requirements. However they must still undergo pregnancy testing as described in this section. Investigators shall counsel WOCBP and male subjects who are sexually active with WOCBP on the importance of pregnancy prevention and the implications of an unexpected pregnancy.

Investigators shall advise WOCBP and male subjects who are sexually active with WOCBP on the use of highly effective methods of contraception. Highly effective methods of contraception have a failure rate of < 1% when used consistently and correctly.

At a minimum, subjects must agree to use one highly effective method of contraception as listed below.

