### 7.1 *Recording of Adverse Events*

At each contact with the subject, the investigator must seek information on adverse events by specific questioning and, as appropriate, by examination. Information on all adverse events should be recorded immediately in the source document, and also in the appropriate adverse event module of the case report form (CRF). All clearly

related signs, symptoms, and abnormal diagnostic procedures results should be recorded in the source document, though should be grouped under one diagnosis.

All adverse events occurring during the study period must be recorded. The clinical course of each event should be followed until resolution, stabilization, or until it has been determined that the study treatment or participation is not the cause. Serious adverse events that are still ongoing at the end of the study period must be followed up to determine the final outcome. Any serious adverse event that occurs after the study period and is considered to be possibly related to the study treatment or study participation should be recorded and reported immediately.

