#### Investigator Reporting to BMS

- All Serious Adverse Events (SAEs) that occur following the subject's written consent to participate in the study through 30 days of discontinuation of dosing must be reported to BMS Worldwide Safety, whether related or not related to study drug. If applicable, SAEs must be collected that relate to any later protocol-specified procedure (e.g., a follow-up skin biopsy).
- Following the subject's written consent to participate in the study, all SAEs, whether related or not related to study drug, are collected, including those thought to be associated with protocol-specified procedures. The investigator should report any SAE occurring after these aforementioned time periods, which is believed to be related to study drug or protocol-specified procedure.
- An SAE report should be completed for any event where doubt exists regarding its seriousness;
- If the investigator believes that an SAE is not related to study drug, but is potentially related to the conditions of the study (such as withdrawal of previous therapy or a complication of a study procedure), the relationship should be specified in the narrative section of the SAE Report Form.
- If the BMS safety address is not included in the protocol document (eg, multicenter studies where events are reported centrally), the procedure for safety reporting must be reviewed/approved by the BMS Protocol Manager. Procedures for such reporting must be reviewed and approved by BMS prior to study activation.

An appropriate SAE form (e.g. ex-US = CIOMS form or USA = Medwatch form) should be used to report SAEs to BMS. If you prefer to use your own Institutional form, it must be reviewed by BMS prior to study initiation. Note: Please include the BMS Protocol number on the SAE form or on the cover sheet with the SAE form transmission.

- The CIOMS form is available at:  
<http://www.cioms.ch/index.php/cioms-form-i>
- The MedWatch form is available at: [MedWatch 3500 Form](#)

- [[contact]](mailto:[contact])
- In accordance with local regulations, BMS will notify investigators of all reported SAEs that are suspected (related to the investigational product) and unexpected (ie, not previously described in the IB). An event meeting these criteria is termed a Suspected, Unexpected Serious Adverse Reaction (SUSAR). Investigator notification of these events will be in the form of a SUSAR Report.

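### The stated AE and SAE windows end 30 days after the last infusion, about when abatacept withdrawal begins, and are not reconciled with AE assessments scheduled to week 48-52

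*Combined protocol and SAP*

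**What the plan says.** **Windows tied to the last dose**
- Section 7.1, Adverse Event Reporting Period: reporting runs "from the initiation of any study procedures to the end of the study treatment follow-up", and for this trial "the study treatment follow-up is defined as 30 days following the last administration of study treatment".
- Section 7.2.1, Investigator Reporting to BMS: SAEs of any causality from consent "through 30 days of discontinuation of dosing must be reported to BMS Worldwide Safety". Later SAEs are asked for if believed related to the drug or to a protocol procedure.
- Recording of Adverse Events (the second section numbered 7.1): all AEs in the study period must be recorded. An SAE after that period is recorded and reported if considered possibly related to the treatment or to participation.

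**Provisions that run longer or set no end**
- Section 3.1, tables of events: the adverse events row is marked at Month 9 and week 48-52 for non-responders and in the table titled "REMISSION OR LOW DISEASE ACTIVITY TABLE OF EVENTS". In the version of that table for patients who flare, it is marked at flare, every 4 weeks and at week 48-52.
- Recording of Adverse Events: at each contact, "the investigator must seek information on adverse events by specific questioning".
- Section 7.1, Non-serious Adverse Event Collection and Reporting: 30 days after the last dose is a minimum. On the start, "The collection of non-serious AE information should begin at initiation of study drug".
- Section 7.2.1, notifying the study sponsor: any type of SAE is reported within 24 hours, with no end date.

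**Follow-up.** Under section 3.1, patients in low disease activity at 6 months are followed off abatacept for 6 months or until flare, ending by week 52.

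**The concern.** Stopping abatacept is the second intervention of this trial, and 17 to 20 of the 25 patients are expected to enter that phase. A window counted from the last dose closes almost exactly when the phase opens, so staff would assess AEs for months with no clear rule on what to do with those not judged related.

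A relatedness filter suits this phase poorly. Section 7.1 defines relatedness by the administration of study drug, and harm from stopping a drug does not fit that definition neatly. Section 7.2.1 gives withdrawal of a previous therapy as an example of a study condition that may cause an SAE not related to study drug, and asks for that link to be explained in the narrative.

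There is little else to catch a gap. Section 3.4 names no safety endpoint, section 6.2 plans no AE summary, section 7.3 (Stopping Rules) has a heading without text, and there is no DSMB.

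**Working it through.** The protocol gives no calendar week for the end of the window, so it has to be derived.

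**Inputs**
- Seven infusions: time 0, week 2, week 4, then every 4 weeks (section 1.5); the Study Summary lists time 0, week 2 and Months 1 to 5.
- Window: last dose + 30 days (sections 7.1 and 7.2.1).
- Withdrawal phase: from week 24 (section 3.3) to week 52 (section 3.1), that is day 168 to day 364, or 196 days.
- Assumption for the second reading: a calendar month of 30.44 days.

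**Closing date**
- Four-weekly: doses at weeks 0, 2, 4, 8, 12, 16 and 20. Last dose on day 140; 140 + 30 = day 170; 170/7 = week 24.3.
- Calendar months: last dose at 5 × 30.44 = day 152; 152 + 30 = day 182; 182/7 = week 26.0.

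**Share of the withdrawal phase outside the window, for a patient followed to week 52**
- Four-weekly: covered 170 − 168 = 2 days; 2/196 = 1%. Outside: 364 − 170 = 194 days = 27.7 weeks, or 99%.
- Calendar months: covered 182 − 168 = 14 days; 14/196 = 7%. Outside: 364 − 182 = 182 days = 26.0 weeks, or 93%.
- If withdrawal is instead counted from calendar month 6 (day 183), none of it is covered.
- If time off drug is counted from the last dose, the 30 days cover 30/224 = 13% (four-weekly) or 30/212 = 14% (calendar months).

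**Scheduled AE assessments after closure**
- Month 9 (9 × 30.44 = day 274): 274 − 170 = 104 days, or 274 − 182 = 92 days, after closure.
- Week 48 (day 336): 166 or 154 days after. Week 52 (day 364): 194 or 182 days after.

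**Reading the passages together.** Adverse Event Reporting Period defines the study period in which AEs must be reported. Recording of Adverse Events makes recording mandatory within a study period and asks for later SAEs only if possibly related. If the term means the same in both places, an unrelated SAE at Month 9 need not be recorded under that section or sent to the manufacturer under section 7.2.1. Yet the table has a visit that asks about AEs, and the other part of section 7.2.1 requires any SAE to go to the sponsor. Nothing says which governs.

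**A complication in the end date.** The flare table also marks abatacept infusion at flare and every 4 weeks. Section 3.1 says abatacept is discontinued after 6 months in all patients, and the Study Summary gives seven infusions. If infusions were given as that table marks them, the last administration would move later and the window would extend or reopen. These passages must be reconciled before the window has a definite end for patients who flare.

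**The case against.** The strongest case against is that the protocol does not shut down safety capture. The 30 days for non-serious AEs is a minimum. SAE reporting to the sponsor has no end date and no relatedness test. Section 7.2.2 sends deaths during the study to the IRB within 72 hours at the latest, related or not. Section 7.1 records new clinically significant findings at the end of the study as AEs, and AEs are sought at each contact. All of this stands, and it rules out several stronger readings that a reader might infer:

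- *AE and SAE reporting stops, or only related events are reportable, after week 24.* The provisions just listed contradict this. The cut-off is explicit only in the general AE reporting period and for SAEs to the manufacturer.
- *The tables and the reporting rule cannot both be followed.* They can: a site may assess AEs at Month 9 and still satisfy a 30-day minimum. The defect is ambiguity, not impossibility.
- *The safety result will cover the treatment phase alone.* That does not follow while AE assessments are scheduled to week 48-52.
- *Half the trial is uncovered for everyone.* The figure of 26.0 to 27.7 of 52 weeks (50-53%) applies only to responders who do not flare. Non-responders leave at 6 months apart from a 9-month visit, and the hold ends at flare.
- *Flare admissions will be lost because of the window.* Section 7.1 has its own rule for hospital stays for the target disease, so their reporting does not depend on the window alone.
- *The window must last at least "5 half-lives of study drug (70 days").* That figure sits in a contraception requirement. It shows that 30 days is shorter than the drug's stated persistence, but the documents do not make it a standard for AE follow-up.

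What the objection does not answer is that none of these provisions sets an end date beyond 30 days for AEs not judged related, and none says which rule prevails.

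**Conclusion.** The concern holds as an internal contradiction with a practical consequence. The AE reporting period and the all-causality SAE window to the manufacturer close at about week 24 to 26. For responders who do not flare, about 26 to 28 weeks of off-drug follow-up lie beyond them. Other sections continue AE assessment through that time, so whether events not judged related must be recorded, reported or analysed is left open, and a site following the narrower sections could omit them.

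The size rests on seven infusions with none after Month 5, on follow-up to week 52, and on whether months are four weeks or calendar months; the range shows both. No power or error-rate figure is involved.

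Two related wording conflicts are secondary. The start of AE collection differs between sections (first study procedure, or first dose for non-serious AEs). The elicitation rule also differs: Recording of Adverse Events asks for specific questioning, while the Adverse Event definition says "subjects should not be questioned regarding the specific occurrence of one or more AEs".

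**What to change.** - In Adverse Event Reporting Period, Non-serious Adverse Event Collection and Reporting, Recording of Adverse Events and section 7.2.1, state one AE/SAE window. Run it from consent or first study procedure to each patient's last study visit (Month 9 or week 48-52, as in the tables), regardless of relatedness.
- State which visit is last for non-responders: section 3.1 describes one visit at 9 months, but their table also marks AEs at week 48-52.
- In section 6.2, tabulate AEs and SAEs separately for the treatment and withdrawal phases, with the number of patients and the patient-time in each, because time off drug will vary with flare.
- Reconcile the infusion marks in the flare table with section 3.1 and the Study Summary, since they change the date of last administration.
- Use one AE elicitation rule throughout.

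The later visits and AE marks already exist, so the cost is protocol wording, some additional AE and SAE forms, and more unrelated events to process. The AE row now starts at Day 1, so a start at consent or first procedure also needs an entry at screening.

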### **Preexisting Condition**

A preexisting condition is one that is present at the start of the study. A preexisting condition should be recorded as an adverse event if the frequency, intensity, or the character of the condition worsens during the study period.

### **General Physical Examination Findings**

At screening, any clinically significant abnormality should be recorded as a preexisting condition. At the end of the study, any new clinically significant findings/abnormalities that meet the definition of an adverse event must also be recorded and documented as an adverse event.

### **Post-study Adverse Event**

All unresolved adverse events should be followed by the investigator until the events are resolved, the subject is lost to follow-up, or the adverse event is otherwise explained. At the last scheduled visit, the investigator should instruct each subject to report any subsequent event(s) that the subject, or the subject's personal physician, believes might reasonably be related to participation in this study. The investigator should notify the study sponsor of any death or adverse event occurring at any time after a subject has discontinued or terminated study participation that may reasonably be related to this study. The sponsor should also be notified if the investigator should become aware of the development of cancer or of a congenital anomaly in a subsequently conceived offspring of a subject that has participated in this study.

### **Abnormal Laboratory Values**

A clinical laboratory abnormality should be documented as an adverse event if any one of the following conditions is met:

- The laboratory abnormality is not otherwise refuted by a repeat test to confirm the abnormality
- The abnormality suggests a disease and/or organ toxicity
- The abnormality is of a degree that requires active management; e.g. change of dose, discontinuation of the drug, more frequent follow-up assessments, further diagnostic investigation, etc.

any laboratory test result that is clinically significant or meets the definition of an SAE

All laboratory test results captured as part of the study should be recorded following institutional procedures. Test results that constitute SAEs should be documented and reported to BMS as such. It is expected that wherever possible, the clinical rather than laboratory term would be used by the reporting investigator (eg, anemia versus low hemoglobin value).

